#### **Tool IV: Social Adjustment Scale Self-Report (SAS-SR):**

The Psychological & Social Adjustment Scale is a measure of psychological and social adjustment that will originally be modified by Weissman in 1999. is a paper-and-pencil selfreport scale that measures instrumental and expressive role performance over the past 2 weeks in adults. The 54-

item assessment covers six areas of functioning, including work (either as a paid worker, unpaid homemaker, or student), social and leisure activities, relationships with extended family, role as a marital partner (if applicable), parental role (if applicable), and role within the family unit (including perceptions of economic functioning). The scores for each domain are calculated as averages, with higher mean scores indicating better psychological and social adjustment. The scale has been found to have high internal consistency with alpha coefficients ranging from 0.78 to 0.89 (Gameroff, Wickramaratne & Weissman, 2012).

**The Preparation Phase**

**Pilot study**

To assess the transparency, objectivity, viability, relevancy, and applicability of the research tools, a pilot study will perform on 20 patients who met the inclusion criteria .The patients in this group will not be included in the study sample. Study tools will test-retest reliability will do for the study tools; The Herth Hope Index (HHI), Psychological &Social Adjustment Scale and Ryff psychological wellbeing scale (PWBS).

**Implementation of the Horticultural Therapy Program**

On each recruited ward patients will interview individually to establish rapport and to apply tool I (A Socio-demographic and Clinical data Structured Interview Schedule) to elicit their sociodemographic and clinical characteristics. Each patient gets detailed explanations in relation to the aim of the study and objectives of the training and tool I, II, III, and IV. The latter two steps will do for the control group to take base line data and cross matching with study group will be applied.

Egyptian Horticultural Therapy Program will develop by researcher in psychiatric nursing and **botanist** (reference) that included planting, watering, follow up, and harvesting plants. It consisted of eight group sessions; a 30-minute session will be conducted once a week for eight weeks. The first introductory session will concern participants sharing their interest in and experiences with plants, defining the goals of HT about their past horticulture experiences. At the end of the first session, a written plan for every session (time, duration, and setting) will be scheduled individually with each patient. Session conduct by two general group as female group and male group.

The therapist emphasized the use of two plants, one that produces a crop (Cloves) and the other one aromatic and floral plant (Lavender). *Insert Table 1*

Session	General objective:	Steps
Opening session	Emphasizing the general aim of	General information about

I-
	
-planting
 
Empowering self-competency to take care of plant
	
-psychosocial benefit of planting.
 
Name the plants with presentable product of Cloves and Levander.
 
Asking about feeling toward plants and process of planting
 
Give detailed brochure about steps of planting.
 
Providing tool of planting -(seeds, seedlings, soil, pots.....)
 
Give note of schedule about daily expression of emotion

II- Beginning of Hope
	
- Learning and practicing planting
 
- Assuring the understanding
	
- ???????

III- It grows green
	
- Learning and practicing propagation skills.
 
- Reflecting on and sharing thoughts about the vitality of plants.
	
- Expression of patients note

IV- Attention and follow up
	
- Focusing on patients' emotions
 
- Practice the emergency care
	
- Debriefing and expression of patient's emotion
 
- Write note about current

	
of planting
	
state. _____

--	--------------------	---------------------

		
 
-
 
- n to the complain about planting.
 

V- Mindfulness: watching, and smell plants tasting ing the	
 
- Experiencing mindfulness techniques during the activities.
 
- sharing thoughts about using this experience in mindful eating, and its potential use as a relaxation activity.
 
	
 
- Present moment awillness of watching, tasting and smelling.
 
- Describe the current view, smell, and taste in a nonjudgment attitude.
 
- Correct the patient’s description as focus on past/ future or previous judgmental talks.
 

VI- Exhibition Garden: collective view	
 
- learning to design a pot garden using various plants and decorations.
 
-
 
	
 
- Present every patient plant.
 
- share thoughts about the feeling of appreciation.
 

VII- Time of harvesting	
 
- Practicing harvesting.
 
	
 
- share the symbolic meaning of harvesting. To share overall feedback about the HT sessions.
 

VIII- Ending session	
 
- Describing overall feedback about the HT sessions.
 
	
 
- Ask about meaning of growing.
 
- Describe benefits and
 

		hazards of planting
--	--	---------------------

### **Evaluation or Follow-up Phase**

The evaluation phase encompassed a post-test assessment after one month and a 3-month followup assessment using the outcome measures administered at baseline that will be conducted for both groups (study and control groups) through interviewing the participants individually to ensure the effectiveness of the HT.

Give the detailed session and material for control group if needed.

### **Statistical analysis plan**

Quantitative data will be analyzed and presented using various statistical measures. To assess the normality of distribution, the Kolmogorov-Smirnov test will be performed. Descriptive statistics such as range (minimum and maximum values), mean, standard deviation, and median will be used to summarize and describe the quantitative data. The significance of the results obtained from statistical tests will be evaluated at the 5% level.

For qualitative data, numbers and percentages will be used to describe and summarize the findings. On the other hand, quantitative data will be summarized using the minimum and maximum values to reflect the range of the data. The mean will be employed as a measure of central tendency in statistical significance testing, while the standard deviation provides information about the variability of the scores in the dataset.

Chi-square test, Monte Carlo test: used to test the significance of result of qualitative variable.

In addition, paired t-test will be used to test the significance of result of normal quantitative variables.

Marginal Homogeneity Test Non-parametric significance tests will be used for two dependent samples and McNemar test significance with two dependent sample studies.

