**Research Hypothesis:**

Patients with psychotic disorders who received Horticultural Therapy exhibited higher psychological wellbeing, Hope, and Social Adjustment than those who didn't receive it.

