**Study method& Procedure**

**Research Design:**

A quasi- experimental research design will be followed.

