### **Participants:**

The G\* Power windows 3.1.9.7 program will be used to estimate the sample size using the following parameters: total sample size around 880, effect size = 0.5,  $\alpha$  err prob=0.05, Power (1- $\beta$  err prob) =0.95, Number of groups=2, Number of measurements=3, Corr among rep measures=0.5. The program estimates a minimum sample size of 54 patients, the researchers decided to recruit 60 patients for the control group and 60 patients for the study group. To be eligible in the study, patients diagnosed with schizophrenia and bipolar disorder with no comorbidity, not in the acute stage, absence of any allergy toward plants, their duration of illness not exceeding 10 years and able to communicate coherently and relevantly as well as can read and write.

A proportionate stratified randomization sample technique from each unit will be obtained using the following formula: Total sample size/ size of the entire population  $\times$  the expected population size of each unit. The required sample size will be selected randomly. Patients of the study group will be randomly subdivided into six groups with ten patients in each group and will receive 8 one-hour group sessions of interventions, in addition to the routine hospital care. The control group will receive routine hospital care only (psychiatric examination, diagnosis, and pharmacotherapy).

A total of 850 participants will be approached, 120 patients will select randomly, 60 for control and study group equal. To ensure that all hospital wards that serve adult patients with psychotic disorders will properly be represented in the study sample, the stratified sampling technique will used through applying the following steps:

- a. The 14 of psychiatric wards will be divided into two strata based on male: female proportion; (8 adult male and 6 adult female wards for psychotic patients).
- b. Considering the male to female wards ratio around (3: 2), random selection of adult psychotic wards will do using simple randomization technique to pick up 50% of these wards (7 wards).
- c. On each randomly selected ward, all patients' medical charts will be screened to identify

patients who met the predetermined inclusion criteria.

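### The only test assigned to the outcome scores is a paired t-test, which does not compare study with control as the hypothesis requires

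*Protocol*

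**What the plan says.** Research Hypothesis: patients given the therapy "exhibited higher psychological wellbeing, Hope, and Social Adjustment than those who" did not receive it. This is a comparison of study with control.

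Participants: the sample size inputs include "Number of groups=2, Number of measurements=3, Corr among rep measures=0.5", and 60 patients are recruited to each arm. Evaluation or Follow-up Phase: both arms are reassessed after baseline, at one month and at 3 months.

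Statistical analysis plan: for scores, a "paired t-test will be used to test the significance of result of normal quantitative variables". The marginal homogeneity test belongs to a sentence that reads "Non-parametric significance tests will be used for two dependent samples and McNemar test significance with two dependent sample studies". Chi-square and Monte Carlo tests are given for qualitative variables only.

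Tools II to IV: PWBS and SAS-SR are averaged scores, and HHI is twelve four-point items. No cut-offs are given for any of them.

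**The concern.** A paired test needs pairs, and the section does not say what is paired. The only pairs that the protocol defines are repeated visits of one patient, so the test measures change within an arm.

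The hypothesis is about the difference between arms. Patients past the acute stage may still change over three months on routine care. A before-after change in the study arm does not estimate study versus control. Nor does a result that is significant in one arm and not in the other. The control arm would then play no part in testing the three outcome scores, and change common to both arms could be reported as a programme effect.

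**Working it through.** **1. The plan's own figure.** The stated inputs (effect size 0.5, alpha 0.05, power 0.95, 2 groups, 3 measurements, correlation 0.5) are said to give 54 patients.
- Repeated-measures ANOVA, between factors, 0.5 read as f: λ = f²·N·m/(1+(m−1)ρ). At N = 38, λ = 0.25×38×3/2 = 14.25 and power is 0.957, so 38 patients are enough. The within and within-between forms give 14.
- A two-sided paired t-test with dz = 0.5 gives 54: noncentrality 0.5×√54 = 3.67, power 0.950.
- A two-group test of one measurement with f = 0.5 (d = 1.0), 27 per arm, also gives 54: noncentrality √(27/2) = 3.67, power 0.950.

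So 54 shows neither which test was meant nor whether 0.5 is d, dz or f. The concern does not depend on this figure.

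**2. Each listed test against the hypothesis.**

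| Test | Assigned to | Compares arms on the scores? |
|---|---|---|
| Paired t | normal quantitative | No, unless cross-arm pairs exist |
| Marginal homogeneity, McNemar | dependent samples | No |
| Chi-square, Monte Carlo | qualitative | Only on score categories, and none are defined |

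The one hint of cross-arm pairing is "cross matching with study group will be applied" (Implementation of the Horticultural Therapy Program). It names no matching variables and no pairs, and Participants describes random picking until each arm reaches 60.

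**3. Size when the programme has no effect (illustrative).** Assume the same drift in both arms, n = 60 per arm and scores in baseline SD units. SD of change = √(2(1−ρ)). Noncentrality = drift×√60/√(2(1−ρ)), with 59 df, two-sided 5%.

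| Correlation | Drift (SD) | Noncentrality | Study-arm paired test significant | Study significant and favourable, control not |
|---|---|---|---|---|
| 0.5 | 0.1 | 0.775 | 0.119 | 0.102 |
| 0.5 | 0.2 | 1.549 | 0.332 | 0.222 |
| 0.5 | 0.3 | 2.324 | 0.628 | 0.234 |
| 0.3 | 0.2 | 1.309 | 0.251 | 0.188 |
| 0.7 | 0.2 | 2.000 | 0.503 | 0.250 |

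The last column is P(study significant and favourable) × P(control not significant). With zero drift the paired test rejects in 5%.

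**4. Baseline-adjusted comparison of arms (ANCOVA, one visit, ρ = 0.5, 117 df).** SE = √(2(1−0.5²)/60) = 0.158 SD, and the 95% CI half-width is 1.98×0.158 = 0.31 SD. Shared drift cancels.
- Rejection is 5% if the arms are comparable given baseline. If they differ by 0.1 or 0.2 SD given baseline, it is 0.096 or 0.241.
- Power at d = 0.5 is 0.88 (noncentrality 0.5/0.158 = 3.16). Power of 0.95 needs 79 per arm. At d = 1.0 power is above 0.99.

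**5. Clustering by therapy group.** Simulated, with the ICC assumed as a share of residual variance in the study arm only. The group term compares baseline-adjusted therapy-group means with control patients, using Satterthwaite df. Values are for ICC 0, 0.05 and 0.10.

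| | Six groups of 10 | Two groups of 30 |
|---|---|---|
| Type I error, no term | 0.050, 0.076, 0.105 | 0.050, 0.137, 0.211 |
| Type I error, with term | 0.052, 0.052, 0.052 | 0.067, 0.092, 0.108 |
| Power at d = 0.5, with term | 0.84, 0.75, 0.68 | 0.69, 0.45, 0.38 |
| Power at d = 1.0, with term | 1.00, 1.00, 1.00 | about 0.9, 0.7, 0.6 |

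With six groups and the term, the mean CI half-width is 0.33, 0.37 and 0.41 SD.

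**The case against.** The strongest reply is that the section is a loose list. It does not claim to be complete, the sample size inputs show that a two-group analysis was intended, and a separate SAP, not shown, may name one. The absence of a between-group test would not by itself be a fault of the protocol. But the section does more than stay silent: it assigns the scores to a paired test, so a later SAP would have to depart from it. Chi-square and cross matching do not rescue the text, because neither cut-offs nor pairs are defined.

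The second reply is that the error rates rest on an assumed drift, which the protocol does not give. That is right. The figures show what could happen and are not measured from the trial. The mismatch between test and hypothesis does not depend on them.

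The third reply is that ANCOVA at a single visit is a choice. This also stands. A mixed model over the three visits would fit the sample size inputs at least as well, provided that one study-control contrast at a named visit is declared as the test. It is also fair that a better test cannot repair unclear allocation or ward effects, and that whether all three scales must succeed remains to be stated.

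**Conclusion.** The concern holds, and the section must be changed before any confirmatory claim is made. The one test assigned to the HHI, PWBS and SAS-SR scores does not answer the study-versus-control hypothesis.

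Under no programme effect and an assumed shared drift of 0.1 to 0.3 SD, false support from the study-arm test runs from 12% to 63% at correlation 0.5. At a drift of 0.2 SD it is 25% at correlation 0.3 and 50% at 0.7. Reading significance in one arm but not the other still gives 10% to 23% at correlation 0.5. These figures assume 60 per arm, normal scores and independent patients.

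A baseline-adjusted comparison removes shared drift. It holds 5% only if the arms are comparable given baseline, and the quasi-experimental design and the selection steps in Participants do not secure this.

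**What to change.** **In Statistical analysis plan:** for one stated score per scale, compare study with control at one named visit by ANCOVA adjusted for the baseline score. Report the study-minus-control difference with its 95% CI. The 3-month follow-up is proposed, because it falls after the eight weekly sessions whether counted from baseline or from programme end. The one-month visit is then secondary. Keep the paired t, marginal homogeneity and McNemar tests as descriptive.

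**In Participants:** state how patients reach study or control, since the adjusted comparison depends on it. State the metric of the effect size.

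**Reconcile the therapy groups first.** Participants says "Patients of the study group will be randomly subdivided into six groups with ten patients in each group"; Implementation says "Session conduct by two general group as female group and male group". If there are six groups, add therapy group as a random effect in the study arm with Satterthwaite df. If there are two, therapy group coincides with sex, and neither including nor omitting the term holds 5% once outcomes cluster. That limit must be stated. Ward effects are not covered by this change: with the arms in separate wards (4 versus 3, assumed), plain ANCOVA rejects in 0.143 and 0.228 of null trials at ward ICC 0.05 and 0.10.

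**Cost:** rewording of one section and a few sentences in another, with no new patients or visits for the analysis itself. The power statement may have to change. If 0.5 means d, 60 per arm gives 0.88 without clustering, and 0.84, 0.75 or 0.68 with the six-group term at ICC 0, 0.05 or 0.10. The sponsor would then restate the 0.95 or recruit more (79 per arm without clustering). If 0.5 means f, power stays above 0.99 with plain ANCOVA or the six-group term.

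### The only test named for the normally distributed scores is a within-arm paired t-test, which neither compares study with control nor uses the baseline score as a covariate

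*Protocol*

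**What the plan says.** The protocol's section Statistical analysis plan names these tests:

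- For normally distributed scores: "paired t-test will be used to test the significance of result of normal quantitative variables".
- For repeated categorical data: a marginal homogeneity test and a McNemar test ("Non-parametric significance tests will be used for two dependent samples and McNemar test significance with two dependent sample studies").
- For categorical data generally: "Chi-square test, Monte Carlo test: used to test the significance of result of qualitative variable".

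No covariate, stratum or model is named, and neither sex nor ward is mentioned.

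Other sections set up a different question:

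- Research Hypothesis predicts higher wellbeing, hope and social adjustment in treated than in untreated patients.
- Evaluation or Follow-up Phase has two later assessments, "using the outcome measures administered at baseline that will be conducted for both groups".
- Participants fixes 60 patients per group and sizes the study with "effect size = 0.5" and "Corr among rep measures=0.5", for two groups and three measurements.
- Participants also builds the sample by sex and ward: "The 14 of psychiatric wards will be divided into two strata based on male: female proportion". Half of the wards (seven) are then drawn at random.
- Research Design calls the study quasi-experimental.

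**The concern.** A paired t-test in the study arm asks whether those patients changed. It cannot separate the programme from routine care, the passage of time or regression to the mean, which is what the control group is for. Running the same test in each arm and comparing the p-values does not test the difference between arms.

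The baseline scores are a second loss. They are collected in both arms, and the protocol commits to a correlation between visits, but the named method uses baseline for these scores only by subtraction within a patient. If the investigators fill the gap in the obvious way and compare mean changes between arms, the protocol's own correlation is the value at which subtraction gains nothing over ignoring baseline. Because the study is called quasi-experimental, baseline differences between arms may also exceed chance, and the section contains nothing that adjusts for them.

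**Working it through.** **Inputs.** 60 per arm, correlation ρ = 0.5 among three measurements, effect size 0.5, power 0.95 (Participants); 5% level ("The significance of the results obtained from statistical tests will be evaluated at the 5% level"). Assumed: two-sided tests and equal variances at each visit, with σ = 1. The metric of the effect size is not stated.

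**The plan's own figure.** Participants gives a minimum of 54.

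- Repeated-measures F test, between-groups effect, f = 0.5, m = 3: λ = N f² m / (1 + (m − 1)ρ) gives N = 38.
- Group-by-time interaction: λ = N f² m / (1 − ρ) gives N = 14.
- Two-group F test on one measurement, f = 0.5: λ = 54 × 0.25 = 13.5 gives power 0.9501, so N = 54.
- Paired t-test with standardised mean change 0.5: 54 pairs.

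So 54 does not follow from all the stated inputs and does not settle the metric. Under the paired reading, the SD of a change is √(2(1 − 0.5)) = 1, so a standardised change of 0.5 is 0.5 SD. If controls did not change, that would be d = 0.5 between arms. Both d = 0.5 and f = 0.5 (d = 1.0 for two equal groups) are therefore carried below.

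**The test that is named (within one arm, n = 60).**

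- Paired: SE = √(2(1 − 0.5)/60) = √(1/60) = 0.129 SD.
- Same two visits treated as unpaired: √(2/60) = 0.183 SD.

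Pairing therefore helps here. The difficulty is the question asked: if both arms drift by an assumed 0.25 SD with no treatment effect, the study-arm paired test is significant about 48% of the time.

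**The comparison that the hypothesis needs (between arms, 60 each).** SE = √(2v/60), where v is the variance relative to the follow-up score:

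| Method | v | v at ρ = 0.5 | SE (SD units) |
|---|---|---|---|
| Follow-up only | 1 | 1.00 | 0.183 |
| Change score | 2(1 − ρ) | 1.00 | 0.183 |
| Baseline as covariate | 1 − ρ² | 0.75 | 0.158 |

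The covariate analysis is worth 60/0.75 = 80 patients per arm analysed without it.

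**Sensitivity to ρ (change score against covariate).** ρ = 0.3: 1.40 against 0.91. ρ = 0.5: 1.00 against 0.75. ρ = 0.7: 0.60 against 0.51. The covariate analysis is better throughout; exact equality of change score and follow-up only is special to 0.5.

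**Power with 60 per arm at ρ = 0.5.**

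- If 0.5 is d: 78.2% for change or follow-up only, 88.5% with the covariate (normal approximation; 77.5% and 88.0% from the t distribution). For 95% power: 104 against 78 per arm.
- If 0.5 is f: above 99.9% in every case.

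**Sex and ward.** The documents give no share of outcome variance for them. If they explained an assumed 0% to 10% of what remains after baseline, the variance would fall from 0.75 to between 0.75 and 0.675. Any benefit would lie mainly in balance.

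**The case against.** The strongest objection is that the 1.00-against-0.75 contrast belongs to a comparison of change scores between arms, which the protocol never names. That is right. A reader might infer that the planned paired t-test gets no precision from baseline; the documents do not support this, since pairing reduces the standard error from 0.183 to 0.129 SD in that test. The no-gain result is conditional on carrying the changes into an arm comparison.

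Other points against:

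- **Left to a separate plan.** Covariates often are. But this section is itself headed as the statistical analysis plan and states a specific test for the scores, which does not answer the stated hypothesis.
- **Arms might be compared otherwise.** The chi-square test could compare arms on categories, but the PWBS and SAS-SR are scored as averages. Implementation of the Horticultural Therapy Program mentions a cross matching of the groups at baseline. If this meant one-to-one pairs, a paired test could compare arms, but no pairs are defined.
- **Strata.** A reader might infer that stratified randomisation is being ignored, or that omitting the strata causes the result at 0.5. Neither follows. Sex and ward are described as steps in drawing the sample, not as strata within which arms are randomised, and the arithmetic at 0.5 does not involve them.
- **Bias.** A reader might infer that change scores always over-correct baseline differences. That is not general. If arms are non-random with stable differences, change scores can be unbiased and covariate adjustment biased, and measurement error at baseline makes covariate adjustment under-correct.
- **Power.** If 0.5 is f, the loss has no practical effect on power. This stands.

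**Conclusion.** The point holds in a limited form. The one test named for normally distributed scores is within-arm. It does not compare study with control and does not use baseline as a covariate, although baseline is collected in both arms.

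The size of the avoidable loss, if changes were compared between arms, is a variance of 1.00 instead of 0.75 (SE 0.183 against 0.158 SD). This rests on ρ = 0.5, equal variances and 60 analysed per arm. It matters for power only on the d reading (about 78% against 88%). A reader might conclude that the trial is underpowered; the documents do not support that, because the metric is unstated and on the f reading power is above 99.9% by either method.

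The case for changing the plan rests first on answering the hypothesis, and then on a precision gain that costs almost nothing. Because the design is quasi-experimental, adjustment can reduce bias from baseline differences but does not guarantee its removal.

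**What to change.** In Statistical analysis plan:

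- For each study-versus-control comparison of HHI, PWBS and SAS-SR, fit a linear model of the follow-up score on arm with the baseline value of the same score as covariate, or a repeated-measures mixed model covering both follow-up visits. Report the adjusted arm difference with its confidence interval.
- Keep the within-arm paired tests as description only.
- Add sex as a factor. Alternatively, use ward fixed effects in place of sex where each ward contains both arms, or fit sex as fixed and ward as random. Do not enter sex and ward together as fixed factors: the wards are single-sex, so ward determines sex and the model would not be estimable. The protocol does not say whether each ward contains both arms, and this should be stated first.
- In Participants, state whether the effect size of 0.5 is d, f or a standardised change, and reconcile 54 with the listed inputs.

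The cost is a few lines of text. The scores and sex are already collected, and ward is known from recruitment. Baseline takes one degree of freedom. Sex takes one, or ward takes six with seven wards (7 − 1), from 118 in a two-group comparison of 120 patients.

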#### **Tool III : Ryff psychological wellbeing scale (PWBS):**

The Psychological Wellbeing Scale (PWBS) was developed by Ryff in 1989 and modified to 18 items. The PWBS consists of seven-point Likert scales for each of its six subscales, which include autonomy, environmental mastery, personal growth, positive relations with others, purpose in life, and self-acceptance. The scores for each subscale are averaged, with higher mean scores indicating greater psychological wellbeing. Studies of psychotic patients have shown that the PWBS has high internal consistency, with alpha coefficients ranging from 0.78 to 0.88 (Mahmud, Islam, & Sharif, 2022).

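### The analysis section names no suitable paired test for an outcome score that fails the Kolmogorov-Smirnov check: its other two paired tests need categories that no tool defines

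*Protocol*

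**What the plan says.** The protocol's Statistical analysis plan states a normality check: "To assess the normality of distribution, the Kolmogorov-Smirnov test will be performed". It then says that a "paired t-test will be used to test the significance of result of normal quantitative variables". For other paired data it says: "Marginal Homogeneity Test Non-parametric significance tests will be used for two dependent samples and McNemar test significance with two dependent sample studies". It names no rank test and does not say what follows when a score fails the check. It gives chi-square and Monte Carlo tests to qualitative variables, makes the mean the measure of central tendency in significance testing, and adds: "The significance of the results obtained from statistical tests will be evaluated at the 5% level".

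The section on the follow-up phase describes assessments at one and three months, "using the outcome measures administered at baseline that will be conducted for both groups". Only the outcome scales are described as repeated; Tool I belongs to the initial interview.

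The scales are numeric. The HHI has twelve four-point items. For the PWBS: "The scores for each subscale are averaged, with higher mean scores indicating greater psychological wellbeing". For the SAS-SR: "The scores for each domain are calculated as averages". None of the three tool descriptions gives a level, category or cut-off.

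**The concern.** McNemar and marginal homogeneity tests compare the distribution of a category between two paired occasions. They do not test a mean, and they do not apply to a numeric score until it has been grouped. The section thus pairs numeric repeated outcomes with categorical paired tests. It also lets a preliminary test, whose result varies from sample to sample, decide whether the one suitable paired test may be used.

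The same scale could pass the check in one arm or visit and fail in another. The analyst would then have to invent a test or a grouping after the data are in. Grouping can cost much power, and the unstated cut decides how much.

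**Working it through.** **1. Which variables the two tests could act on**

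| Variable | Repeated? | Type as described | Levels defined? |
|---|---|---|---|
| Tool I | no, initial interview only | mixed | natural categories |
| HHI | yes | 12 four-point items | none for the scale |
| PWBS | yes | subscale means | none |
| SAS-SR | yes | domain means | none |

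No variable is both repeated and categorical at the level of a scale or subscale. So there are two readings. Either the two tests are idle and a non-normal score has no named test, or the scores are grouped at points not given. Each leaves a gap in the stated analysis.

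**2. Inputs for the size**

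The protocol gives no power figure for any test in this section, so there is none to reproduce. Its minimum of 54 patients is a separate calculation and is not used here.

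- From the protocol: 60 patients per group, so at most 60 pairs within a group; correlation 0.5 among repeated measures; 5% level; planned power ("err prob) =0.95, Number of groups=2").
- Assumed: two-sided testing; a shift of 0.5 SD (the protocol gives an effect size of 0.5 without naming its metric), with 0.37 SD as a smaller alternative; score shapes and cut positions.

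**3. Near-normal scores, shift 0.5 SD**

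*Paired t-test.* The SD of the difference is √(2(1 − 0.5)) = 1, in units of the score SD. The noncentrality is 0.5 × √60 = 3.87 against a critical t of 2.00 (59 df). Power is 97%.

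*McNemar, cut at the baseline mean.* The share below the cut is 0.500 before and Φ(−0.5) = 0.309 after. The bivariate normal gives 0.273 moving up and 0.082 moving down. Over 60 pairs that is 16.4 against 4.9 discordant pairs. Summing over the binomial distribution of discordant pairs gives power 74% (exact test 66%).

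*McNemar, cut 1 SD above the baseline mean.* Moving up 0.211, down 0.061, or 12.7 against 3.7 pairs. Power is 63% (exact 54%).

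Simulation with the same inputs agrees to within about a point and adds the other tests:

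| Test | Shift 0.5 SD | Shift 0.37 SD |
|---|---|---|
| Paired t | 97% | 80% |
| Wilcoxon signed-rank | 96% | 78% |
| Marginal homogeneity, three levels at tertiles | 87% | 63% |
| McNemar, cut at mean (exact) | 74% (65%) | 50% (40%) |
| McNemar, cut 1 SD above (exact) | 63% (54%) | 38% (29%) |
| McNemar, cut 1 SD below (exact) | 42% (31%) | 26% (18%) |

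**4. Skewed scores (gamma), shift 0.5 SD**

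This is the case that the check would more often divert.

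| Test | Shape 2 | Shape 4 |
|---|---|---|
| Paired t | 96% | 96% |
| Wilcoxon | 98% | 97% |
| McNemar, lower-quartile cut (exact) | 99% (98%) | 89% (84%) |
| McNemar, median cut (exact) | 91% (87%) | 84% (77%) |
| McNemar, upper-quartile cut (exact) | 61% (52%) | 61% (52%) |
| Marginal homogeneity, tertiles | 98% | 93% |
| Marginal homogeneity, thirds of the scale range | 53% | 81% |

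Against Wilcoxon, the loss runs from none to about 98 − 52 = 46 points. At 0.37 SD and shape 2 the worst case is Wilcoxon 84% against exact McNemar 28%, a loss of 56 points.

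**5. How often the check would divert a score (n = 60)**

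For roughly normal integer scores, the uncorrected Kolmogorov-Smirnov test rejects in about 0% of samples and the Lilliefors version in 12-24%. For the skewed scores the rates are 6-21% and 64-85%. The protocol does not say which version is meant.

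**The case against.** A reader might infer that the protocol plans to dichotomise its outcomes with a large loss of power. The text does not support that. It nowhere says that scores will be grouped, and its statement that means are used in testing points the other way. Nor is a large loss general: the near-normal figures describe scores that would mostly pass the check, and for skewed scores some cuts cost nothing. A claim of inflated false positives from cut-offs picked after seeing the data would also go too far, since nothing in the protocol suggests that practice.

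Other defences can be raised. The sentence on dependent samples is garbled and could be a general promise of non-parametric tests, with the names left to a separate plan. Marginal homogeneity can be run on single Likert items without a cut. The unclear reference to cross matching at baseline might mean paired patients, so that the two tests would apply to Tool I categories.

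These points limit the claim but do not remove it. None of them supplies a suitable named paired test for a non-normal numeric score. Item-level tests would not analyse the subscale or domain means by which the PWBS and SAS-SR are scored.

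**Conclusion.** The point holds as a mismatch between named tests and data. The paired t-test is conditional on a Kolmogorov-Smirnov result, the only other tests named for dependent samples are categorical, and the repeated outcomes are numeric with no categories defined.

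The power cost is conditional on the scores being cut, which the protocol does not state. It also depends on the assumed shift, the score shape, the cut and the version of the test. With near-normal scores and a 0.5 SD shift, every grouped analysis examined falls below the planned 95%. With skewed scores it may or may not. Sixty complete pairs is the best case. The simulations treat patients as independent and so ignore delivery in groups of ten.

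This should be corrected, but it does not by itself invalidate the trial.

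**What to change.** - Do not let the Kolmogorov-Smirnov result choose the test.
- Analyse the HHI, PWBS and SAS-SR always as numeric scores, by one method fixed in advance. It should compare the two groups, because the research hypothesis concerns treated against untreated patients. A baseline-adjusted ANCOVA or a mixed model over the visits would serve.
- Add a rank or bootstrap analysis as a sensitivity check on distribution.
- Remove McNemar and marginal homogeneity tests from the outcome analysis. Keep chi-square and Monte Carlo tests for categorical Tool I variables.
- If score levels are wanted, show them descriptively only, with cut-offs written down in advance.

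The cost is a few lines of text in the analysis section, with no extra patients, visits or data.
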